We will enroll eligible prostate patients who were diagnosed between 2010 and 2019 and are being followed within radiation and medical oncology clinics at the MedStar Georgetown University Hospital (MGUH) and MedStar Washington Hospital Center (MWHC). In this initial pilot, we will not focus on newly diagnosed patients but instead will focus on patients who are being followed for a number of reasons: 1) Substantial numbers of patients who are currently being followed have now become candidates for genetic testing based on updated guidelines and 2) This will allow us to maximize our potential sample size within the one year framework of this grant, allowing us to obtain preliminary efficacy data in preparation for a planned multisite R01 study of newly diagnosed patients with high risk localized or metastatic disease. By providing information particularly salient to prostate cancer patients, reducing barriers to genetic testing and proactively facilitating genetic testing delivery, we expect that our proactive and streamlined approach will yield increased uptake of genetic testing. Our specific aims are:

- 1: **Evaluate the impact of ST vs. UC on genetic testing uptake.** *H1.1:* Patients randomized to ST will be more likely to complete genetic testing compared to UC. *H1.2:* Participants randomized to ST will make better informed genetic testing decisions (characterized by high knowledge, risk comprehension and concordance with attitudes) compared to UC. *H1.3:* Few patients in the ST arm will opt for traditional genetic counseling prior to testing.
- 2: **Evaluate patient satisfaction and psychosocial outcomes in ST vs. UC.** *H2.1:* Compared to UC, those randomized to ST will be more satisfied with their genetic testing decision and will have less decisional regret.
- 3: **Evaluate the impact of ST vs. UC on uptake of cascade testing in unaffected family members.** In exploratory analyses designed to provide effect size estimates, we will compare the arms on rates of genetic testing in relatives of patients found to carry a PV.

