## **4.0 Study Endpoints\***

### **4.1 Primary and secondary endpoints:**

1. Genetic test uptake
2. Receipt of pre-test genetic counseling
3. Psychosocial outcomes (Satisfaction, distress, decision regret)
4. Use of cascade testing among unaffected family members of mutation carriers

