## **6.0 Procedures Involved\***

6.1-6.4 The objective is to develop and pilot a novel streamlined approach to deliver genetic education and testing to the rapidly increasing number of prostate cancer patients who meet guidelines for genetic referral. Our streamlined genetic testing approach is designed to facilitate genetic education and testing for men with prostate cancer. The intervention will incorporate proactively delivered print educational materials in lieu of pre-test genetic counseling. The materials will increase awareness, expand access, provide

balanced information to foster informed genetic testing decisions and reduce barriers to facilitate the delivery of genetic testing. All men who are found to carry a PV or variant of uncertain significance (VUS) in a cancer risk gene will have an individual telephone genetic counseling disclosure session with a board-certified genetic counselor. We will recruit 120 prostate cancer survivors who meet clinical referral criteria. After a baseline survey, we will randomize participants to: ST vs. UC. Participants will complete a follow-up survey at 2-3-months post-randomization. Our primary outcome is genetic testing uptake.

Eligibility and Accrual. Men eligible for this study are currently being followed at MGUH or MWHC for either:

Metastatic prostate cancer;  
Gleason 7+ prostate cancer.

We will exclude patients who have had, or are already scheduled for genetic counseling or testing for *BRCA1* or *BRCA2* mutations. We will also exclude men who cannot participate in English and provide meaningful consent. We will recruit participants from medical and radiation oncology clinics at MGUH and MWHC. These clinics currently follow well over 1000 eligible patients.

Gender and Minorities. Participants will be adult men. Given the racial/ethnic breakdown of the clinics we are recruiting from. We expect that at least 30% of participants will be members of racial/ethnic minority groups.

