Recruitment. Working with our clinical collaborators and the Survey, Recruitment and Biospecimen Collection Shared Resource (SRBSR) will obtain contact information of potentially eligible patients from clinical databases and/or the EMR. We will mail an introductory letter describing the study (from the study MPIs and the patient's physician), opt-out postcard/phone number, informed consent document and a print version of the baseline survey to all potentially eligible participants. We will also email electronic versions of these materials for patients who prefer to complete them online. Two-weeks following this mailing, an SRBSR research assistant (RA) will call patients who have neither opted out nor completed the baseline survey. For men who have not returned the consent document, we will use an IRB-approved verbal consent for completing the baseline survey and request return of the written consent prior to randomization. Following completion of print or electronic consent and the baseline survey, the RA will randomize participants. Men randomized to ST will be sent a priority mail packet with detailed genetic testing educational material. Men randomized to UC will be mailed a letter informing them that they meet guidelines for genetic counseling and provided with contact information to schedule a genetic counseling appointment with a LCCC genetic counselor.

Randomization. Following completion of the baseline survey and consent document, an RA will randomize participants via computer-generated random numbers in blocks of 8 and a ratio of 1:1. Participants will be notified of their random assignment via letter and email.

**Assessments.** We will administer baseline (T0) and 2- to 3-month (T1) follow-up telephone/electronic surveys. Genetic testing uptake will be assessed via clinical records and basic clinical and demographic information abstracted from the EMR. See Table 1 for assessment instruments and schedule of administration.

Table 1. Measures		T0	T1
Variables	Measures		
Covariates/Background Variables	Demographics, clinical variables, family history (EMR/survey)	X	
Health Literacy	Brief Health Literacy Screening Tool	X	
Genetic Test Uptake	Study Records		X
Knowledge/Risk Comprehension	Genetic Knowledge Scale and Perceived Mutation Risk.	X	X
Attitudes	Adapted version of the Multimodal Measure of Informed Choice (MMIC), Fatalism, Medical Mistrust Index	X	
Decision Regret	Decisional-Regret Scale.		X

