Decision Satisfaction	Satisfaction with Decision Scale.		X
Distress	Cancer distress: PROMIS Anxiety and Depression; Genetic testing distress MICRA.	X	X
Quality of Life/Functional Status	PROMIS Physical Function and Social Function Short Forms	X	X
Cascade Testing	Number of relatives who have proceeded with genetic testing.		X

**Streamlined Testing (ST) Intervention.** Men randomized to ST will be sent a priority mail packet with the ST print education materials and information on how to proceed with genetic testing. ST participants will have the option of proceeding directly to genetic testing or scheduling a telephone genetic counseling session. The content of the ST intervention is described in section 5.0 above.

**Usual Care (UC).** After completion of the baseline survey, UC participants will be sent a letter from their physician indicating that they meet eligibility criteria for genetic testing, recommending that they schedule genetic counseling and providing a contact telephone number to schedule their session. Patients may opt for free telephone genetic counseling.

**Genetic Testing.** Participants who choose to pursue genetic testing will be offered a standard clinical multigene panel of at least 40 genes, including *BRCA* and genes associated with potential differential diagnoses (e.g., Lynch syndrome). All testing will be performed by Invitae, a CLIA certified clinical lab not affiliated with the GLCCC. Invitae offers genetic testing free of charge to eligible prostate cancer patients (all study participants will be eligible for free genetic testing through Invitae). Prior to proceeding with genetic testing, participants will be required to sign and return a clinical genetic testing consent form, after which we will mail them an at-home DNA kit for saliva collection which will be returned directly to Invitae (shipping costs are pre-paid).

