**Aim 3: Evaluate the impact of ST vs. UC on uptake of cascade testing in unaffected family members.** In exploratory analyses designed to provide effect size estimates for our planned R01, we will use t-test to compare the ST to UC on the number of relatives of PV carriers who undergo cascade genetic testing.

**Power:** Power estimates are for 2-tailed tests ( $\alpha=.05$ ). The study is powered based on our primary outcome of patient genetic testing uptake. We expect no attrition since data will be abstracted from clinic records. With no relevant studies on which

Table 2. Sample Size Calculation			
	ST Uptake		
UC Uptake	.40	.45	.50
10%	39	25	20
15%	49	36	27
20%	81	54	39

to base our effect sizes for this pilot study, Table 2 displays the necessary sample size (per group) to obtain 80% power for a range of potential clinically significant effects on test uptake (40%-50% for ST; 10%-20% for UC). Based on this analysis, we will enroll 120 participants in order to attain 80% power to detect a clinically meaningful difference between 20% in UC and 45% in ST. For our secondary outcomes, a sample size of 120 and 10% attrition at 3-months (n=108 in final sample) will provide  $> 80\%$  power to detect medium sized effects of  $d=.54$  SDs on our secondary outcomes (e.g., decisional conflict, patient satisfaction). This effect size is well within the range that we have seen in previous studies and represents an effect that is generally considered to be clinically significant.

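### Aim 3 promises rates of cascade testing in unaffected relatives, but the plan measures and tests a count with no stated denominator

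*Combined protocol and SAP*

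**What the plan says.** The documents describe Aim 3 in four places.

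- **Section 2.0, Aim 3.** The aim is to "Evaluate the impact of ST vs. UC on uptake of cascade testing in unaffected family members". The sentence that follows says "we will compare the arms on rates of genetic testing in relatives of patients found to carry a PV".
- **Section 4.1, endpoint 4.** "Use of cascade testing among unaffected family members of mutation carriers".
- **Section 6.0, Table 1, Cascade Testing row.** The measure is "Number of relatives who have proceeded with genetic testing", marked at T1 only.
- **Section 17.1, Aim 3.** The heading again names unaffected family members. The analysis reads "In exploratory analyses designed to provide effect size estimates for our planned R01, we will use t-test", and the test is to "compare the ST to UC on the number of relatives of PV carriers who undergo cascade genetic testing".

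On timing, section 6.0 says "Participants will complete a follow-up survey at 2-3-months post-randomization". Table 1 also lists family history from the EMR or survey at T0 as a background variable. No section says that it counts eligible or already tested relatives, and none links it to Aim 3.

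**The concern.** A rate needs a number tested and a number who could have been tested. The plan names only the first. A carrier's count is roughly his number of eligible relatives multiplied by uptake per relative, so a difference in mean counts cannot be separated into family size and uptake. Uptake is what the aim asks about.

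The Table 1 wording also sets no starting point for counting and no limit to unaffected relatives. Earlier testing is plausible in these families. The Study Summary and section 25.1 let men with Gleason 7+ disease qualify through a family history of breast, ovarian, pancreatic or prostate cancer, and section 2.0 calls testing established care for women with breast and ovarian cancer. Within the 2 to 3 months to T1, the patient must consent, return a kit and get his result before any relative can act on it. True cascade counts will therefore probably be small, and one earlier test could weigh heavily.

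The stake is the effect size for the planned R01, which is the only stated purpose of Aim 3. If eligible relatives and the timing of their tests are not recorded at T1, no other data source named in the plan supplies them.

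**Working it through.** **1. The plan's own figure.** Aim 3 has no sample size or effect size of its own. The carrier counts below rest on the planning rates for the primary outcome, so those are checked first. For UC 20% v ST 45%, two-sided 0.05 and 80% power, with pooled variance under the null:

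n = [1.96 × √(2 × 0.325 × 0.675) + 0.842 × √(0.20 × 0.80 + 0.45 × 0.55)]² / 0.25² = (1.298 + 0.537)² / 0.0625 ≈ 53.9, so 54 per group. This matches Table 2. Enrolment of 120 at 1:1 gives 60 per arm.

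**2. Expected carriers** = 60 × uptake × PV prevalence. Section 3.0 gives prevalence as up to 17%; the 10% and 5% rows are assumptions that show the range. The last two columns are binomial probabilities with n = 60.

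| PV prevalence | ST carriers | UC carriers | P(at least 2 in both arms) | P(no UC carrier) |
|---|---|---|---|---|
| 17% | 60 × 0.45 × 0.17 = 4.59 | 60 × 0.20 × 0.17 = 2.04 | 0.58 | 0.13 |
| 10% | 2.70 | 1.20 | 0.26 | 0.30 |
| 5% | 1.35 | 0.60 | 0.05 | 0.55 |

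These are before survey attrition. At the 10% allowed in section 17.1, the 17% row becomes 4.59 × 0.9 = 4.1 and 2.04 × 0.9 = 1.8.

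**3. What family size does to a count.** The documents give no family size, no uptake among relatives and no rate of earlier testing. What follows is hypothetical: 5 ST and 2 UC carriers, a mean of 6 eligible relatives, and 30% uptake per relative in both arms, so no true effect. With F the number of eligible relatives and p the uptake per relative:

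Var(count) = E[F] p(1 − p) + p² Var(F)

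Var(difference in mean counts) = (1/5 + 1/2) × Var(count) = 0.7 × Var(count)

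- Var(F) = 6: 6 × 0.21 + 0.09 × 6 = 1.80. SD of the difference = √(0.7 × 1.80) = 1.12 relatives.
- Var(F) = 20: 6 × 0.21 + 0.09 × 20 = 3.06. SD = √(0.7 × 3.06) = 1.46 relatives.

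The mean count is 6 × 0.30 = 1.8, so these SDs are 62% and 81% of it. The expected difference is zero. Family size supplies 0.54/1.80 = 30% to 1.80/3.06 = 59% of the count variance. At Var(F) = 12 the share is 26% for p = 0.15 and 67% for p = 0.5.

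**4. Adding earlier tests.** If 10% of the relatives not otherwise tested had been tested earlier and were counted, the proportion counted becomes 0.30 + 0.70 × 0.10 = 0.37. The SD of the difference is then √[0.7 × (6 × 0.37 × 0.63 + 0.37² × Var(F))], which is 1.46 at Var(F) = 12 and 1.70 at Var(F) = 20.

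**5. The rate instead.** Simulating tested/eligible under the same assumptions gives a difference centred on zero with SD 0.16 to 0.18, or 54% to 59% of the 30% rate (0.163/0.30 and 0.178/0.30). The rate answers the question asked and is somewhat steadier, but it remains very imprecise.

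**The case against.** **Cascade testing already implies the right relatives and the right timing.** The term ordinarily means testing prompted by the patient's result, and the Table 1 row, the endpoint and the aim heading all point that way. A reader might infer from the Table 1 wording that any relative ever tested will be counted. The documents do not say that. What stands is narrower: the measure's wording does not exclude affected relatives or earlier tests.

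**Randomisation protects the comparison.** A reader might infer that family size and earlier testing will drive the arm difference. That is not shown. If family size has the same distribution among carriers in each arm, the expected count difference under equal uptake is zero, as in the working. Carriers are, however, a subset formed after randomisation: men who chose testing, at rates expected to differ by arm, and who tested positive. Balance among them is not guaranteed, and with about 5 v 2 families chance imbalance can be large.

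**The survey may ask more.** The T1 questionnaire is not reproduced and Table 1 is a one-line summary. The point is therefore about the plan as written. Even if the survey asks for eligible relatives, section 17.1 analyses the number.

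**The plan's other rules may help.** Section 17.1 puts covariates that differ by arm at p < 0.10 into final models, but a two-sample t-test takes no covariates. Aim 2 turns to a more descriptive account if PV carriers are too few; Aim 3, which rests entirely on carriers, has no such fallback.

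**The family-history route is unsettled.** Sections 6.0 and 10.2 do not require family history for Gleason 7+ men, and metastatic patients qualify without it. This weakens any forecast of how common earlier testing will be, but not the gap in the measure.

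**The repair does not cure scarcity.** This is correct. Too few carriers limits the effect size at least as much as the choice of metric.

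**Conclusion.** The mismatch holds on the text. A rate in unaffected relatives is promised, a number of relatives is listed and tested, and no denominator or counting window is stated. Followed as written, the plan cannot produce the promised rate.

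The size of the consequence is less certain. About 4.6 ST and 2.0 UC carriers are expected, assuming the 45% and 20% planning uptakes, the upper 17% prevalence and no survey attrition. At lower prevalence there are fewer. In groups of that size, chance differences in family size or earlier testing can distort the count difference. No systematic bias is demonstrated, and the family-size figures above are illustrations under stated assumptions, not forecasts.

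Severity is low. Aim 3 is exploratory and does not affect the primary outcome. It is still worth correcting, because the aim exists to supply effect sizes and the missing items are cheap to collect.

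**What to change.** - **Measure (Table 1, T1).** For each PV carrier, record the number of living unaffected adult relatives eligible for testing, within a stated degree of kinship, and how many of them were tested after the patient's result. State whether relatives tested before that result are left out of the denominator; if so, a third item should count them.
- **Analysis (section 17.1, Aim 3).** Replace the t-test on counts with a descriptive report of tested/eligible by arm, with intervals that treat the family as the unit. If an arm has fewer than two carriers, list its families without an interval.
- **Interpretation.** State in advance that the small number of carriers makes any Aim 3 effect size very imprecise, and that the planned R01 should not rely on the point estimate alone.
- **Wording.** Use the same population and metric in section 2.0, section 4.1, Table 1 and section 17.1.

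The cost is two or three survey items for about seven men (4.59 + 2.04 = 6.6) and a short text change. The downsides are slight respondent burden, reliance on the patient's report of when relatives were tested, and no p-value for a comparison of roughly 5 v 2 families.

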### 17.2 Data Security: Our plan for maintaining confidentiality is as follows:

The protection of privacy of participants in studies related to genetic risk information is of the utmost importance. Our plan to maintain confidentiality is as follows: 1) We will minimize communication that involves names or other identifying information. Where this is unavoidable, communications will be made via express mail, on a study dedicated fax machine, or via HIPAA compliant, access protected and SSL encrypted REDCap data capture system. 2) Clinical information such as personal and family cancer history and genetic testing results will not be communicated together with names in any written materials for study-related communication or data storage. However, as part of standard clinical practice, participants who opt for testing will receive a genetic testing report generated by the lab that will contain their name and other identifying information. This report will also be sent to the participant's treating physician as per standard clinical practice. Similarly, the genetic counselors' summary letters will contain participants' names, test results, and other identifying information. 3) All paper documents will be securely stored in the participant's research file, which will be kept in a locked cabinet in research team offices within secure buildings. 4) Information obtained during or as a result of this study will not be released without

the written consent of the participating individual. 5) In all data sets, including those with genetic counseling and testing info, we will use ID numbers only. A separate data set linking names with ID numbers will be accessible only through password protected and secure data programs and available only to trained staff.

*17.3* Quality assurance reviews will be conducted throughout the course of the study to ensure data quality and protocol adherence.

*17.4* Data Handling: Personal information will only be used to contact potential study participants. This information will not be stored with the survey data. Only a code number will be used to identify study-related data. A matching list will be created as a cross-reference for contact information and data.

Matching lists of names and code numbers will be kept in locked storage facilities in the PI's office and/or laboratory space. All data will be similarly stored in locked facilities. All computer files containing participant data will be accessed only through password protected security systems and are stored on a secure and private server used by the Cancer Prevention and Control Program at LCCC. Further, procedures for ensuring data integrity and security will be reviewed at regular intervals through team meetings between the PI and other members of the study team. Ethical issues and topics related to the responsible conduct of research will be also be discussed routinely with the overall study team, including the potential for adverse events, data safety and data management, handling misconduct, etc.

Only the PI, research staff and data managers will have access to this information. Transfer of information will occur via the HIPAA compliant and fully secure REDCap system and through the HIPAA compliant and fully secure Georgetown Box system.

Protected Health Information (PHI) that will be collected includes: lab results, interviews/questionnaires, data previously collected for research purposes under another approved GU or MedStar IRB study, and from a database.

All study-related data will be stored in the secure REDCap system and within Georgetown Box. Only study investigators will have access to this information. All access to study-related data will be via password protected and encrypted access. Data from this study will be stored for seven years after the final publication from the study. During this time, the PI will be responsible for approving access to the study data. Any computer used to access the study-related data will have active and up to date software in place to protect against malware, all operating systems and software updates and patches will be applied regularly and two factor authentication will be in place for all systems accessing research data

## **18.0 Provisions to Monitor the Data to Ensure the Safety of Subjects\***

This research does not involve more than minimal risk to subjects.

